#### **5.6.4      Loss to follow-up**

For patients whose status is unclear because they fail to appear for study visits without stating an intention to withdraw, the investigator should show "due diligence" by contacting the patient, family or family physician as agreed in the informed consent and by documenting in the source documents steps taken to contact the patient, e.g. dates of telephone calls, registered letters, etc.

A patient cannot be considered as lost to follow-up until the time point of his/her scheduled end of study visit has passed.

#### **5.6.5      Early study termination by the sponsor**

The study can be terminated by Novartis at any time for any reason. This may include reasons related to the benefit risk assessment of participating in the study, practical reasons, or for regulatory or medical reasons (including slow enrolment). Should this be necessary, the patient must be seen as soon as possible and treated as a prematurely withdrawn patient. The investigator may be informed of additional procedures to be followed in order to ensure that adequate consideration is given to the protection of the patient's interests. The investigator will be responsible for informing the Institutional Review Board/Independent Ethics Committee (IRBs/IECs) of the early termination of the trial.

### **6           Visit schedule and assessments**

[Table 6-1](#) lists all of the assessments and indicates with an "x" when the visits are performed.

Patients must be seen for all visits on the designated day, or as close to it as possible as allowed "visit window" of "x" days. Missed or rescheduled visits should not lead to automatic discontinuation. Patients who prematurely discontinue the study for any reason should be scheduled for a visit as soon as possible, at which time all of the assessments listed for the final visit will be performed. At this final visit, all drugs should be reconciled for compliance purpose and the adverse event and concomitant medications reconciled on the eCRF.

Patients/subjects will be contacted for safety evaluations during the 30 days following the last administration of study treatment.

**Table 6-1 Assessment schedule**

| Period   | Screening f) |                      | Titration     |               | Maintenance   |                 |                 |   |
|--|-------------------------|----------------------|---------------|---------------|---------------|-----------------|-----------------|---|
| Visit number   | 1 (Screening)           | 2 (BL) g) | 3             | 4             | 5             | 6               | 7               | 8/disc
continu
ation
h) |
| Visit Day  | -28 ~ -14               | 1                    | 28            | 56            | 84            | 112             | 140             | 168   |
| Visit week   | -4 ~ -2                 | 1                    | 4             | 8             | 12            | 16              | 20              | 24  |
| Visit Window   | -56 ~ -14               | -7
~
1         | 21
~
35 | 49
~
63 | 77
~
91 | 105
~
119 | 126
~
154 | 161
~
182                             |
| Inclusion/Exclusion criteria   | X                       | X                    |               |               |               |                 |                 |   |
| Obtain Informed consent  | X                       |                      |               |               |               |                 |                 |   |
| Patient demographics/other baseline characteristics                                      | X                       | X                    |               |               |               |                 |                 |   |
| Problem of previous ChE inhibitors treatment a)                               | X                       | X                    |               |               |               |                 |                 |   |
| Medical history  | X                       |                      |               |               |               |                 |                 |   |
| Previous treatment/concomitant medication/therapy  | X                       | X                    | X             | X             | X             | X               | X               | X   |
| Brain scan if required b)   | X                       |                      |               |               |               |                 |                 |   |
| MMSE   | X                       | X                    |               | X             |               |                 |                 | X e)                             |
| NPI-10   |                         | X                    |               | X             |               |                 |                 | X e)                             |
| QOL-AD   |                         | X                    |               |               |               |                 |                 | X e)                             |
| J-CGIC   |                         |                      | X             | X             |               | X               |                 | X e)                             |
| Modified Crichton Scale  |                         | X                    | X             | X             |               | X               |                 | X e)                             |
| Adverse events   |                         | X                    | X             | X             | X             | X               | X               | X   |
| Vital sign   | X                       | X                    | X             | X             | X             | X               | X               | X   |
| Laboratory evaluation
Regular hematology, blood chemistry, cholinesterase, urine test | X                       |                      |               |               |               |                 |                 | X   |
| Additional Screening blood test for differential diagnosis if necessary                  | X                       |                      |               |               |               |                 |                 |   |
| ECG  |                         | X                    |               |               |               |                 |                 | X   |
| Formulation usability questionnaire c)  |                         |                      |               |               |               |                 |                 | X   |
| Treatment compliance d)   |                         |                      | X             | X             | X             | X               | X               | X   |

(a) Based on the short interview to caregiver by the physician, however, inclusion and exclusion will be judged by physician. This is confirmatory information from caregiver for screening the patients.

(b) Imaging test can be performed at screening visit if latest imagings of a patient are more than 3 years old from baseline.

(c) Based on answer of questionnaire from the caregiver

(d) Based on the interview and assessment by investigators

(e) These assessments are not mandatory at discontinuation due to adverse events

(f) During the screening period, patients will continue receiving their previous medication (donepezil or galantamine)

(g) At the baseline visit, patients discontinue their previous ChE inhibitors (donepezil, galantamine) and could start the initial dose of 9 mg/day rivastigmine patch after cleared all necessary assessment for enrollment. If patients already take their previous ChE inhibitors on the day of baseline visit, the patients should start the initial dose of 9 mg/day rivastigmine patch on the following day (Day 1).

(h) If a patient discontinues the study, scheduled assessment should be performed as soon as possible, but visit window is not set.

## **6.1 Information to be collected on screening failures**

For patients who provided written informed consent but did not complete the baseline visit (withdrawn during the screening period), the investigator will record the withdrawal until baseline visit on the Screening Log, and will record the patient identifier, age, gender and the reason for not being registered on the eCRF.

## **6.2 Patient demographics/other baseline characteristics**

The following items should be investigated at the day of obtaining informed consent to baseline visit or before. Then, the other necessary items such as prior medication, MMSE, vital signs, ECG, and laboratory tests should be investigated or conducted for confirming eligibility.

### **Patient demographics**

Investigate the following items, and record the results in the clinical record and the eCRF. About medical history, only diseases which are related to the Inclusion/Exclusion Criteria or which are judged significant by investigator will be investigated and recorded. Record the problems associated with prior use of oral anti-AD medications

### **Investigation items**

Sex, date of birth, family history, relation of caregiver, date of diagnosis, date of disease onset, years of education, living situation, height, weight, current medical condition, medical history, problems with administration of oral anti-AD medications, [REDACTED]

Additionally, diagnosis of dementia of Alzheimer's type (DSM-IV, NINCDS-ADRDA, NINDS-AIREN) and MHIS should be investigated and recorded in the source document.

### **Brain scan**

A brain scan (MRI or CT) is required at screening but only if one has not been performed in the last three years prior to baseline although the brain scan within one year prior to baseline is preferable. Taking into account the patient burden, these previous brain scan data can be used to confirm diagnosis if the signed informed consent of the patient and legal representative allow the use of this data. Alternatively, if at screening a PET or SPECT is available, which had been performed in the last three years, any MRI or CT conducted in the past will be sufficient.

These scans are performed to establish that entry criteria are met. As outlined above, with the consent of the patient, scans performed before the study will be allowed to reduce the patient burden.

### **Screening Test (Laboratory test) if necessary**

The special laboratory tests are to be performed to exclude non-Alzheimer type dementias during the screening period.

### **Investigation items**

Folic acid, vitamin B12, triiodothyronine (T3), total thyroxine (T4), and thyroid stimulating hormone (TSH)

### **Methods of collection, processing and storage of blood samples**

Approximately 9-mL sample of venous blood will be collected in an AutoSep vacutainer for each patient. After blood sampling, each investigator should follow the blood test procedure of each study site where he/she belongs to.

## **6.3 Treatment exposure and compliance**

### **Previous treatment**

At screening and baseline visit, all treatments which had been received within 4 weeks before and during the screening period, will be reviewed and record name of drug and therapy, dosage and administration, period/duration and reasons for use in the eCRF.

### **Concomitant medication/therapy**

Record the drug names, dosage and administration, period/duration and reasons for use in the eCRF for all treatment used concomitantly during treatment period.

## **6.4 Efficacy**

To ensure the sensitivity and reliability of the efficacy assessments, the same rater for a given instrument will, whenever possible, assess the status of a given patient in every evaluation. All efficacy assessments will be conducted as specified in [Table 6-1](#). The result of these assessments will be recorded in the eCRF. All efficacy assessments at discontinuation will not be conducted if patients discontinue because of an adverse event.

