### **6.4.1 Mini-Mental state examination (MMSE)**

MMSE will be conducted at Visit 1, 2, 4 and 8 (refer [Table 6-1](#)). MMSE at premature discontinuation will not be conducted if patient discontinues because of adverse event.

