#### **6.4.2 Neuropsychiatric Inventory-10 (NPI-10):**

NPI-10 will be conducted at Visit 2, 4 and 8 (refer [Table 6-1](#)). NPI-10 at premature discontinuation will not be conducted if patient discontinues because of adverse event.

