#### **6.4.3 J-CGIC (Japanese version of the Clinical global impression of change)**

J-CGIC will be conducted at Visit 2, 3, 4, 6 and 8 (refer [Table 6-1](#)). J-CGIC at premature discontinuation will not be conducted if patient discontinues because of adverse event.

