#### **6.4.4 Quality of Life- Alzheimer's Disease (QOL-AD)**

QOL-AD will be conducted at Visit 2, and 8 (refer [Table 6-1](#)). QOL-AD at premature discontinuation will not be conducted if patient discontinues because of adverse event.

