**6.4.5 Modified Crichton Scale**

Modified Crichton scale will be conducted at Visit 2, 3, 4, 6 and 8 (refer [Table 6-1](#)). Modified Crichton scale at premature discontinuation will not be conducted if patient discontinues because of adverse event.

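### The protocol gives two rules for efficacy scales when a patient stops for an adverse event, and no planned mean-change analysis varies the missing-data assumption for these patients

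*Protocol*

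**What the plan says.** **Data collection.** Protocol 6.4 first says "All efficacy assessments will be conducted as specified in" Table 6-1, then adds: "All efficacy assessments at discontinuation will not be conducted if patients discontinue because of an adverse event". For the primary scale, 6.4.1 says: "MMSE at premature discontinuation will not be conducted if patient discontinues because of adverse event". Sections 6.4.2 to 6.4.5 say the same of NPI-10, J-CGIC, QOL-AD and the Modified Crichton Scale. Footnote (e) of Table 6-1, attached to all five scales in the Visit 8/discontinuation column, says: "These assessments are not mandatory at discontinuation due to adverse events".

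**Schedule.** After baseline, MMSE is planned only at Week 8 (Visit 4) and Week 24 (Visit 8).

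**Analysis.** The primary analysis is an MMRM of change from baseline under MAR (Protocol 9.4.2 and 9.4.3; SAP 2.5.2 and 2.5.3). The supportive analyses of mean change are the same type of MMRM in the per-protocol and 3-step sets (SAP 2.5.4 only), a completer t-test and an LOCF t-test (Protocol 9.4.4; SAP 2.5.4). The FAS needs a baseline and any post-baseline assessment on treatment, not specifically an MMSE (Protocol 9.1; SAP 2.2). SAP Section 4, point 3, assigns the last record of a discontinued patient to the nearest planned visit.

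**The concern.** Six body sections rule the assessment out, and one footnote in the table they refer to allows it. A site could follow either, so whether an MMSE exists for a patient who stops for an adverse event may depend on the site.

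Either way, primary-endpoint data are lost for a reason linked to tolerating the patch. In a single-arm trial the Week 24 mean change is the main result. If these patients do worse than their observed data predict, the reported mean is too favourable for the whole treated group. The planned analyses would not show how far it depends on the assumption made for them. The direction and size of any departure are unknown.

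**Working it through.** **1. The plan's own figure.** Protocol 9.8 takes SD 3.0 and a 95% half-width of 0.6. n = (1.96 × 3.0 / 0.6)² = 96.04, rounded up to 97, which matches the stated number. Enrolment is 120.

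**2. What each analysis does with a patient who stops for an adverse event**, if the body text is followed and no later off-drug MMSE is taken:

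| Analysis | Stops before Week 8 | Stops after Week 8 |
|---|---|---|
| MMRM (FAS, and per-protocol or 3-step set if included) | no change value, so no record | Week 8 record; Week 24 handled under MAR |
| Completer t-test | omitted | omitted |
| LOCF t-test | nothing post-baseline to carry | Week 8 value carried to Week 24 |

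The first column follows from the SAP 5.3.1 code, which models change, and from SAP 2.1.1.4, which computes change only where both values exist. Such a patient can still be in the FAS. LOCF is not a MAR method, but it makes one fixed assumption (no change after the last value). No analysis varies the assumption.

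**3. Illustrative size.** Inputs:
- Rate of stopping for an adverse event: 16/107 = 14.95%, from the 1-step arm of study 1303 (Protocol 1.1). The exact (Clopper-Pearson) 95% interval is 8.8% to 23.1%.
- Expected number: 0.1495 × 120 = 17.9, about 18 (11 to 28).
- Shortfall relative to the MAR prediction: 1, 2 or 3 points. The documents give no such figure, so this is an assumption.

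Shift in the mean over all 120 = rate × shortfall:

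| Shortfall | Shift | Over the interval for the rate |
|---|---|---|
| 1 | 0.15 | 0.09 to 0.23 |
| 2 | 0.30 | 0.18 to 0.46 |
| 3 | 0.45 | 0.26 to 0.69 |

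A shift as large as 0.6 needs a shortfall of 0.6 / 0.1495 = 4.0 points, or 4.0 / 3.0 = 1.3 SD.

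Among patients with an MMRM record, shift = shortfall × late stops / (120 − early stops). The documents give no timing, so with 18 stops:
- all after Week 8: 18/120 gives 0.15, 0.30, 0.45;
- half before Week 8: 9/111 gives 0.08, 0.16, 0.24;
- all before Week 8: 0, because these patients are absent from the model.

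**4. Would the planned analyses reveal a shift?** A simulation used 120 patients, a 16/107 rate of stopping for an adverse event, SD 3.0, an assumed between-visit correlation of 0.5, and assumed mean changes under MAR of +0.3 at Week 8 and −0.5 at Week 24. Half of the stops came before Week 8.
- Shortfall 0: true mean −0.50; MMRM −0.50, completers −0.50, LOCF −0.43.
- Shortfall 2: true mean over all patients −0.80; MMRM −0.51, completers −0.51, LOCF −0.44.

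The three results hardly move, so their agreement with each other would not be evidence that the MAR assumption is harmless.

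**The case against.** The strongest reply is that the contradiction and the MAR question are separate. None of the figures above measures the effect of the wording conflict, and the MAR question would remain if the footnote matched the text. An MMSE taken at discontinuation is re-mapped to the nearest planned visit, so it would seldom be a Week 24 value. The study is open-label and descriptive with no success criterion (Protocol 3.2 and 9.4.2), MMRM under MAR is a reasonable primary method, and LOCF already steps outside MAR. The 15% comes from a study not described as a switch population. Here, patients who do not tolerate 1-step titration may move to 3-step titration or stay on a lower dose (Protocol 3.1 and 5.1.1). All of this stands, and it limits the size of the point. It does not remove the contradiction, and it does not supply an analysis that varies the assumption.

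Several stronger readings are tempting but not supported:
- *Section 6 is a third conflicting rule.* It asks for all final-visit assessments after premature discontinuation for any reason, but it relies on Table 6-1 and can be read as importing footnote (e).
- *These patients certainly have no Week 24 MMSE.* Protocol 5.6.2 says that stopping the drug is not withdrawal, and SAP 2.6.2.2 expects some patients to remain more than 30 days after stopping. A later scheduled MMSE is neither clearly required nor excluded.
- *LOCF is undefined for early stops.* SAP 2.1.1.4 largely answers this, since change needs a post-baseline value, although it does not name LOCF.
- *The plan forbids further sensitivity analyses.* The sentence in Protocol 9.4.3 and SAP 2.5.3 excluding other imputation follows the description of the primary MMRM, and LOCF is planned anyway.
- *The responder rate in SAP Section 4 is compromised.* Its handling of a missing Week 24 value could be stated more clearly, but a plain reading keeps such patients in the FAS denominator as not meeting the definition.

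**Conclusion.** The contradiction between Protocol 6.4 to 6.4.5 and Table 6-1 footnote (e) is real and must be reconciled. Followed as written, the body text discards MMSE data from patients who stop because of an adverse event, and no planned analysis of mean change varies the assumption made for them. Under the borrowed 15% rate and assumed shortfalls of 1 to 3 points, the Week 24 mean moves by 0.15 to 0.45 points over all 120 patients. Among those with an MMRM record it moves by 0.08 to 0.24 if half stop before Week 8. Both lie below the planned half-width of 0.6.

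A reader might infer that the primary estimate is biased or invalid. The documents do not support that: neither the sign nor the size of a departure from MAR is known, reaching 0.6 at the 15% rate would take an extreme shortfall, and there is no success criterion to overturn. The conclusion is that the estimate is harder to interpret than it need be.

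**What to change.** 1. **One data-collection rule.** Reconcile Table 6-1 footnote (e) with Protocol 6.4 and 6.4.1 to 6.4.5, and have Section 6 point to the result. Preferably the MMSE is done at the discontinuation visit whatever the reason, where the patient is able and consents. This mainly adds records before Week 24 for the MMRM and LOCF and will seldom give a Week 24 score. Cost: a short amendment and one brief test at a visit that already takes place. It is a slight burden on patients who have just had an adverse event, and some will decline.

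2. **One supportive analysis in SAP 2.5.4.** Impute the Week 24 change by multiple imputation under MAR, including FAS patients with no post-baseline MMSE. Then shift the imputed values of those who stopped for an adverse event by −1, −2 and −3 points, and report the mean and confidence interval at each step. Cost: a little programming and one table. It needs no new data, so it remains possible even if data collection can no longer change.

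3. **Optional clarifications.** State how a missing Week 24 value counts in the responder rate, and whether the nearest planned visit means the nearest visit with a scheduled MMSE. State whether patients who stop the drug but stay in the study have the Week 24 MMSE, and that the exclusion of other imputation methods concerns the primary MMRM only.

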### **6.4.1 Mini-Mental state examination (MMSE)**

MMSE will be conducted at Visit 1, 2, 4 and 8 (refer [Table 6-1](#)). MMSE at premature discontinuation will not be conducted if patient discontinues because of adverse event.

#### **Assessment Items**

The MMSE is a brief, practical screening test for cognitive dysfunction. The MMSE consists of 2 parts: language (time orientation, registration and attention) and performance (recall, response to written/verbal commands, writing ability and reproduction of complex polygons), and the total possible score is 30. Lower score indicates more severe impairment ([Folstein MR et al, 1975](#)).

#### **Method of assessment**

Throughout the study, the same rater (an attending physician of a given patient, a psychologist, or a medical staff who has been trained in psychologist equivalent and carried out MMSE scoring more than 50 times) will assess the status of a given patient whenever possible.

#### **6.4.2 Neuropsychiatric Inventory-10 (NPI-10):**

NPI-10 will be conducted at Visit 2, 4 and 8 (refer [Table 6-1](#)). NPI-10 at premature discontinuation will not be conducted if patient discontinues because of adverse event.

##### **Assessment Items**

The NPI-10 is a scale for neuropsychiatric symptoms. The NPI assesses a wide range of behaviors encountered in dementia patients to provide a means of distinguishing frequency and severity of behavioral changes, and facilitates rapid behavioral assessment through the use of screening questions ([Cummings et al. 1994](#)). Ten behavioral domains are evaluated through an interview of the caregiver. The scale includes both frequency and severity ratings of each domain as well as a composite domain score (frequency x severity). The sum of the composite scores for the 10 domains yields the NPI-10 total score. A higher score indicates more severe impairment.

